1. INTRODUCTION AND BACKGROUND

The MiSight® 1 day is the only current soft contact lens with a US-FDA indication to slow the progression of myopia (nearsightedness) in children between the ages of 8 and 12 years old at the initiation of treatment. Johnson and Johnson Vision Care (JJVC) has developed a series of soft contact lens prototypes with novel optical designs that aim to maximize myopia control efficacy while minimizing potential visual impact. The EMO-118 design was efficacious in slowing refractive error progression and axial elongation in children between 7 and 12 years of age after 6 months of wear (████████) and is being confirmed in a longer-term myopia control clinical trial (████████). The EMO-114 design was efficacious in slowing axial elongation and performed similarly to EMO-116, a dual focus myopia control design, but did not demonstrate a statistically significant reduction in refractive error progression at 6 months (████████).^{5,6} EMO-114 did, however, minimize the potential visual impact and provided objective and subjective visual performance that approached a control lens with conventional optics. This study will assess the visual performance of these EMO-118 and EMO-114 in neophyte and habitual soft contact lens wearers compared to a marketed control indicated to slow the progression of myopia.

1.1. Name and Descriptions of Investigational Products

One commercially available marketed product with conventional optics (1-DAY ACUVUE® MOIST) will be used during the study run-in period for neophyte and existing soft contact lens wearers.

This study will test two senofilcon A-C3 design prototypes with varying myopia control optical designs (Test 1 and Test 2) and one commercially available marketed product for myopia control (Control). Both Test lenses are senofilcon A-C3 prototypes and use the same manufacturing process as the ACUVUE OASYS® Brand Contact Lenses with HydraLuxe™ Technology (AO1D; cleared by FDA under K042275). The Test lenses have a smaller lens diameter and a steeper base curve compared to the AO1D to facilitate lens application while maintaining a well-centered fit in children. While both Test lenses have myopia control optical designs, the EMO-114 lens has a larger optical zone, no central myopic defocus dot and reduced dioptric power within the myopia control zones. The Control lens is manufactured in omafilcon A material and features two concentric zones to create myopic defocus.

Further details about the test articles are found in section 6 of this protocol. For detailed information regarding the investigational products, refer to the latest version of the Investigator's Brochure for EMO Design Family Lenses and the package insert of the marketed products.⁷

1.2. Intended Use of Investigational Products

The intended use of the investigational products is for correcting myopia and slowing the progression of myopia in children. For this study, however, slowing the progression of myopia is not a study endpoint and the duration of test article wear may not produce a lasting effect. During the study, each test article will be worn bilaterally in daily wear, daily disposable

Clinical Study Protocol

Johnson & Johnson Vision Care, Inc.

modality for at least 8 hours per day. The subject will wear each investigational product for one wearing period.

1.3. Summary of Findings from Nonclinical Studies

All previous pre-clinical findings were deemed satisfactory prior to proceeding with clinical trials on humans. For the most comprehensive nonclinical information regarding EMO-114 and EMO-118 refer to the latest version of the Investigator's Brochure for EMO Design Family Lenses.⁷

1.4. Summary of Known Risks and Benefits to Human Subjects

The anticipated clinical benefit of the investigational lenses during this study will be the correction of refractive error. While the Test and Control lenses feature myopia control optical designs, the duration of wear during the study is may not be sufficient to produce a lasting reduction in a subject's axial length and myopia control efficacy is not an endpoint of this study. Other potential benefits are that soft contact lenses (conventional and myopia control) have shown better subjective performance versus glasses regarding appearance, satisfaction, social self-perception, and willingness to try new activities.⁸

The anticipated risks associated with the use of the investigational lenses are considered to be the same as those for any other soft contact lens worn in the same modality (i.e. daily disposable wear) and within the same population.

While the target population for this study is children (<18 years), not adults, clinical research has generally supported that younger children can successfully and safely wear soft contact lenses.⁹⁻¹² While contact lens wear is less common in children than adults, studies assessing adverse event rates have concluded that the adverse event rates in children are similar to established rates among adults wearing soft contact lenses.^{9,10} A thorough review of the risks and benefits of myopia control concluded that the incidence of corneal infiltrative events and microbial keratitis in children 12 years of age and younger is no higher than that observed in adults, and may be lower.⁹ Furthermore, all investigational lenses used in this study will be used in a daily wear, daily disposable modality, which reduces lens care burden and avoids potential contamination from the storage case, a known risk factor for microbial keratitis.^{13,14}

Another known risk is that the optical design of myopia control soft contact lenses may not provide equivalent vision quality to a conventional spherical lens design. While minimal difference has been measured between optical designs using high contrast visual acuity, reductions in low contrast and/or low luminance conditions have been reported.¹⁵ While the visual experience with a soft myopia control contact lens may be different, children using MiSight 1 Day have subjectively rated their overall vision similarly to a parallel control group using single vision spectacles after 12 and 24 months of wear.⁸ To manage this risk, the protocol is designed to ensure that each subject meets a minimum visual acuity and reports acceptable subjective vision prior to study contact lens dispense.

No additional risks associated with participation in this investigation are anticipated.

Clinical Study Protocol

Johnson & Johnson Vision Care, Inc.

For the most comprehensive risk and benefit information regarding the EMO lenses refer to the latest version of the Investigator's Brochure for EMO Design Family Lenses and the package insert of the marketed products.

1.5. Relevant Literature References and Prior Clinical Data Relevant to Proposed Clinical Study

The review of the scientific literature examined the current state of published information of contact lens safety and myopia control with soft contact lenses. Potential applicable literature was identified through a literature search on PubMed.org dated since 1980's, as well as through examination of review articles published on the subject. A list of relevant literature references is provided in latest version of the Investigator's Brochure for EMO Design Family Lenses.

To date, there have been five clinical studies completed involving the EMO-118 or EMO-114 lenses (██████████) and there is one additional study that is ongoing (████). █████ (adult) and █████ (pediatric) were both non-dispensing pilot studies with a primary objective of evaluating the visual performance of multiple EMO lens design prototypes. █████ was a non-dispensing study including pediatric and young adult subjects assessing the accommodative response with multiple EMO optical designs. █████ and █████ (ongoing) were myopia control efficacy clinical trials in 7-12 year old children with lenses dispensed for 6-months and, at a minimum, 3 years, respectively. While █████ included both EMO-118 and EMO-114, only EMO-118 was included in █████. Lastly, █████ is an ongoing pediatric non-dispensing clinical study evaluating the vision performance and lens fit acceptance.^{5,6,16-19}

For detailed information regarding prior clinical data refer to the latest version of the Investigator's Brochure for EMO Design Family Lenses and the package insert of the marketed products.⁷

2. STUDY OBJECTIVES, ENDPOINTS AND HYPOTHESES

2.1. Objectives

Primary Objective

The primary objective is to evaluate the logMAR visual performance of soft contact lenses featuring myopia control optical designs.

Exploratory Objectives

The exploratory objectives of the study are to assess:

- logMAR visual performance at 4 m under varying luminance and contrast conditions
- logMAR visual performance at 40 cm under high and low contrast conditions
- Patient-reported outcomes at fitting and follow-up
- Assess safety through adverse events, slit lamp findings, and subject-reported ocular symptoms
- Number of power modifications and over-refraction with first trial lens at fitting

Clinical Study Protocol

Johnson & Johnson Vision Care, Inc.

- Over-refraction at follow-up
- Lens fitting characteristics

2.2. Endpoints

Primary efficacy endpoint:

- Binocular distance (4 m) high luminance high contrast (HLHC) logMAR visual acuity, measured per [REDACTED]

Primary safety endpoint:

- Number (n, %) of subjects and eyes with contact lens related (i.e., related and possibly related) serious and significant ocular adverse events (AEs), including best corrected logMAR loss ≥ 0.20 logMAR (10 letters).

Other exploratory endpoints:

- Monocular HLHC logMAR visual acuity at 4 m
- Binocular high luminance low contrast (HLLC) logMAR visual acuity at 4 m
- Monocular HLLC logMAR visual acuity at 4 m
- Binocular low luminance high contrast (LLHC) logMAR visual acuity at 4 m
- Monocular LLHC logMAR visual acuity at 4 m
- Binocular HLHC logMAR visual acuity at 40 cm
- Binocular HLLC logMAR visual acuity at 40 cm
- Subjective vision, comfort, and ease of handling
- Non-significant AEs and non-ocular AEs
- Slit lamp findings per the ISO 11980 grading scale
- Subject-reported ocular symptoms
- Number of contact lens insertion attempts per eye at fitting
- Subjective best sphere over-refraction with the first trial lens
- Subjective best sphere over-refraction at follow-up
- Number of power modifications at fitting
- Lens fitting characteristics

2.3. Hypotheses

The primary hypothesis must be met to satisfy the objective of the study.

Primary Hypothesis

1. The distance (4 m) binocular high luminance high contrast visual acuity (in logMAR) with EMO-118 will be non-inferior to that of MiSight at follow-up visit. A non-inferiority margin of 0.05 logMAR will be used.

Clinical Study Protocol

Johnson & Johnson Vision Care, Inc.

Other Exploratory Hypotheses

1. The distance (4 m) binocular high luminance high contrast visual acuity (in logMAR) with EMO-114 will be superior to that of EMO-118 at follow-up visit.
2. The distance (4 m) binocular high luminance high contrast visual acuity (in logMAR) with EMO-114 will be superior to that of MiSight at follow-up visit.

3. TARGETED STUDY POPULATION

3.1. General Characteristics

Healthy male and female subjects between 7 and 17 years old with best sphere refraction from -1.00 to -4.50 D (inclusive) and 0.75 D or less astigmatism will be recruited. The goal is to have the number of 7-12 year old subjects approximately equal to the number of 13-17 year old subjects, which will be stratified per site. Potential subjects can be spectacle lens wearers, current soft lens wearers, or symptomatic myopes (e.g., with complaints of blurry vision) currently without correction. There are no restrictions regarding race/ethnicity of the subjects.

3.2. Inclusion Criteria

Potential subjects must satisfy all of the following criteria to be enrolled in the study:

Inclusion Criteria following Screening

The subject must:

1. Read (or be read to) and sign the CHILDREN'S ASSENT (Information and Assent Form) and receive a fully executed copy of the form.
2. Have parents or legal guardians who must read, understand, and sign the STATEMENT OF INFORMED CONSENT (Parental Permission Form and Authorization to Use and Disclose Medical Information).
3. Appear able and willing to adhere to the instructions set forth in this clinical protocol.
4. Be between 7 and 17 (inclusive) years of age at the time of screening.
5. By self-report, habitually wear soft contact lenses or be a current non-contact lens wearer interested in soft lens wear.

Inclusion Criteria following Baseline Evaluation

6. The non-vertex corrected best sphere distance refraction must be between -1.00 D and -4.50 D (inclusive) in each eye.
7. The magnitude of the cylindrical component of the subject's vertex-corrected distance refraction must be less than or equal to 0.75 D (inclusive) in each eye with any degree of axis.
8. The distance visual acuity with best sphere distance correction must be 20/25 or better in each eye.
9. Have \leq 1.50 D difference in subjective best-sphere refraction between the two eyes.
10. Have 20/40 or better vision in each eye with wearable spectacles or uncorrected.

Clinical Study Protocol

Johnson & Johnson Vision Care, Inc.

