3.3. Exclusion Criteria

Potential subjects who meet any of the following criteria will be excluded from participating in the study:

Exclusion Criteria following Screening

The subject must not:

1. Be currently pregnant or lactating.
2. Be diabetic.
3. Be currently using any ocular medications. Lubricants (artificial tears) eyedrops are allowed.
4. Have any current ocular infection of any type.
5. Have any systemic disease (e.g., Sjogren's Syndrome), allergies, infectious disease (e.g., hepatitis, tuberculosis), contagious immunosuppressive diseases (e.g., HIV), autoimmune disease (e.g., rheumatoid arthritis), any underlying medical condition that makes subjects at risk of severe COVID complications, a history of serious mental illness or seizures, or other diseases, by parent or legal guardian's self-report, which are known to interfere with contact lens wear and/or participation in the study.
6. Use of systemic medication (e.g., chronic steroid use) that are known to interfere with contact lens wear and/or participation in the study. See section 9.1 for additional details regarding excluded systemic medications.
7. Have habitually worn rigid gas permeable (RGP) lenses, orthokeratology lenses, or hybrid lenses (e.g. SynergEyes, SoftPerm) within the past 30 days.
8. Be currently wearing lenses in an extended wear modality.
9. Be currently wearing soft contact lenses for astigmatism in either eye.
10. Have participated in a contact lens or lens care product clinical trial within 7 days prior to study enrollment.
11. Be an employee (e.g., Investigator, Coordinator, Technician) or immediate family member of an employee (including partner, child, parent, grandparent, grandchild or sibling of the employee or their spouse) of the clinical site.
12. Children who are wards of the State or any other agency, institution, or entity.

Exclusion Criteria following Baseline Evaluation

The subject must not:

13. Have any ocular allergies, infections, or other ocular abnormalities that are known to interfere with contact lens wear and/or participation in the study. This may include, but is not limited to, entropion, ectropion, chalazia, recurrent styes, glaucoma, history of recurrent corneal erosions, aphakia, moderate or above corneal distortion, herpetic keratitis.
14. Have grade 3 or greater palpebral conjunctival observations or any other grade 2 slit lamp findings on the ISO 11980 classification scale.
15. Have strabismus (intermittent or constant) or amblyopia.

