4.2. Study Design Rationale

This study is to evaluate logMAR visual performance of three soft contact lenses featuring myopia control optical designs using a 3x3 crossover design. Crossover designs are well-established and expose subjects to multiple treatments during different time periods. This design is cost effective and efficient since it eliminates between-subject variability from the treatment comparisons. A limitation of crossover design is the potential for carryover effects between treatments. Since the primary endpoint of logMAR visual acuity is an objective measure, a carryover effect is less concerning. All subjects will begin with a run-in period

Clinical Study Protocol

Johnson & Johnson Vision Care, Inc.

using a single vision contact lens design to allow both new and existing contact lens wearers to enter the study and acclimate to a similar contact lens design.

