5.2. Masking

This is a single-masked study with the subjects being masked. The subjects will not be told any information regarding the optical designs of the lenses beyond that they are intended to correct for their refractive error and feature myopia control optics. The investigators cannot be completely masked to the identity of the investigational lenses because there will be more than one fitting guide used and the fitting guide is specific to the lens design.

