When placed on the cornea in its hydrated state, the MiSight daily wear single use (omafilcon A) Soft (Hydrophilic) Contact Lens acts as a refracting medium to focus light rays on the retina and to simultaneously provide an optical stimulus to slow the progression of myopia.

INDICATIONS FOR USE

MiSight 1 Day (omafilcon A) Soft (Hydrophilic) Contact Lenses for Daily Wear are indicated for the correction of myopic ametropia and for slowing the progression of myopia in children with non-diseased eyes, who at the initiation of treatment are 8-12 years of age and have a refraction of -0.75 to -4.00 diopters (spherical equivalent) with ≤ 0.75 diopters of astigmatism. The lens is to be discarded after each removal.

CONTRAINdications

Do not use the MiSight daily wear single use lens when any of the following conditions exist:

- Acute and subacute inflammation or infection of the anterior chamber of the eye.
- Any eye disease, injury, or abnormality that affects the cornea, conjunctiva, or eyelids.
- Severe insufficiency of lacrimal secretion (dry eyes).
- Corneal hypoesthesia (reduced corneal sensitivity), if not aphakic.
- Any systemic disease that may affect the eye or be exaggerated by wearing contact lenses.
- Allergic reactions of ocular surfaces or adnexa that may be induced or exaggerated by wearing contact lenses or use of contact lens solutions.
- Any active corneal infection (bacterial, fungal, or viral).
- If eyes become red or irritated.
- The patient is unable to follow lens handling and wear regimen or unable to obtain assistance to do so.

Clinical Study Protocol

Johnson & Johnson Vision Care, Inc.

WARNINGS

Patients should be advised of the following warnings pertaining to contact lens wear:

- **PROBLEMS WITH CONTACT LENSES COULD RESULT IN SERIOUS INJURY TO THE EYE.** It is essential that patients follow their eye care practitioner's directions and all labeling instructions for proper use of lens. Eye problems, including corneal ulcers, can develop rapidly and lead to loss of vision. If a patient experiences eye discomfort, excessive tearing, vision changes, or redness of the eye, the patient should be instructed to immediately remove lenses and promptly contact his or her eye care practitioner.
- **WATER ACTIVITY**
 - Do not expose the contact lenses to water while wearing them.

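### Children who already wear MiSight, the control lens, are eligible; prior adaptation to that one lens is not removed by sequence balancing, though its size is unknown and it works against the EMO lenses

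*Combined protocol and SAP*

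**What the plan says.** Section 3.2, criterion 5, requires that the child "By self-report, habitually wear soft contact lenses or be a current non-contact lens wearer interested in soft lens wear". Section 3.1 adds: "Potential subjects can be spectacle lens wearers, current soft lens wearers, or symptomatic myopes".

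The lens-related exclusions in section 3.3 are:
- criterion 7: "Have habitually worn rigid gas permeable (RGP) lenses, orthokeratology lenses, or hybrid lenses", with a 30-day lookback;
- criterion 8: lenses worn as extended wear;
- criterion 9: "Be currently wearing soft contact lenses for astigmatism in either eye".

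Section 9 disallows topical atropine, orthokeratology and vision therapy, among others. None of these provisions names a myopia-control soft lens.

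Section 1 describes the control: "The MiSight® 1 day is the only current soft contact lens with a US-FDA indication to slow the progression of myopia". Its package insert (Appendix C) covers children starting treatment at 8 to 12 years with -0.75 to -4.00 D. The trial enrols ages 7 to 17 with -1.00 to -4.50 D.

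Habitual lens type is recorded at Visit 1, step 1.4. It is not used for eligibility or for stratification, which is by site and age (section 5.1). It is not named in the primary model (section 14.5), which has lens type, sequence, period and first-order carryover as fixed effects. On carryover, section 4.2 says: "Since the primary endpoint of logMAR visual acuity is an objective measure, a carryover effect is less concerning". On masking, section 5.2 says: "This is a single-masked study with the subjects being masked".

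**The concern.** A child who arrives wearing MiSight has already adapted to its optics and found them tolerable. The same child meets the two EMO designs as new lenses. This is a subject-by-lens effect that predates the study and belongs to one of the three lenses. Section 4.2 and the Williams design deal with carryover from one study period to the next, which is a different matter. The protocol does not discuss prior experience of the control lens.

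Two comparisons are exposed: EMO-118 minus MiSight (the primary non-inferiority hypothesis) and EMO-114 minus MiSight (one of the two exploratory superiority hypotheses). The descriptive summaries of subjective vision and comfort are exposed too, and probably more than high-contrast acuity. They depend on the child's own judgement, and a child who recognises a familiar lens is less well masked when giving it.

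**Working it through.** **1. Can a MiSight wearer enrol?** Criterion 5 admits the child, criteria 7 to 9 and section 9 do not exclude the child, and the label's age and power ranges overlap the trial's. So yes, if the other criteria are met.

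**2. Does the design remove the effect?** Let a share f of subjects read d logMAR better (lower) on MiSight because of prior wear. In every sequence the expected EMO-118 minus MiSight difference then rises by

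shift = f × d.

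Because the shift is the same in all six sequences, averaging over them leaves it intact. A simulation of the six-sequence design (54 subjects, correlation 0.3, with subject, period, lens and carryover terms) confirms this:

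| f | d | Expected shift | Simulated shift |
|---|---|---|---|
| 0 | – | 0 | 0.0002 |
| 10% | 0.05 | 0.005 | 0.0048 |
| 20% | 0.05 | 0.010 | 0.0099 |
| 20% | 0.10 | 0.020 | 0.0204 |

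A main effect for habitual lens would not remove it either, since the effect is an interaction with lens type.

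**3. Reproduce Table 8 (section 14.2).** Inputs from the protocol: SD 0.084 for both lenses, margin 0.05, two-sided 5% (upper bound tested at 0.025), correlation ρ of 0.3 or 0.5, paired t-test, n = 50.

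- SD of the difference = 0.084 × √(2(1 − ρ)): 0.0994 at ρ = 0.3 and 0.0840 at ρ = 0.5.
- Standard error = SD/√50: 0.01406 and 0.01188.
- Noncentrality = (0.05 − true difference)/SE, with 49 degrees of freedom and critical t = 2.010.

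At a true difference of 0 the noncentrality is 3.557 or 4.209, and power is 93.7% or 98.5%, as in Table 8. All 12 cells of the table reproduce to within 0.1 point.

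**4. Add a shift.** Neither f nor d is in the documents. The products below are assumptions chosen to show a range, starting from a true difference of 0.

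| Assumed f × d | Shift | Power, ρ = 0.3 | Power, ρ = 0.5 |
|---|---|---|---|
| none enrolled | 0 | 93.7% | 98.5% |
| 10% × 0.02 | 0.002 | 91.7% | 97.7% |
| 20% × 0.035 | 0.007 | 85.1% | 94.4% |
| 20% × 0.05 | 0.010 | 79.7% | 91.0% |

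The 0.010 row matches Table 8's own rows for a true difference of 0.01. A mixture of wearers and non-wearers also adds f(1 − f)d² to the variance of the difference. In the last row that is 0.2 × 0.8 × 0.05² = 0.0004, which takes power to 78.1% or 89.4%.

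**5. Direction.** Adaptation moves the difference toward the margin from below, so the non-inferiority test becomes stricter. With f = 10%, d = 0.05 and ρ = 0.3, the one-sided error at a true difference of 0.05 falls from 0.025 to 0.011.

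**The case against.** The case for leaving the plan alone is substantial.

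- **The effect on acuity may be very small.** Section 1.4 says that high-contrast acuity has differed little between optical designs, and the primary endpoint is high-contrast acuity. An advantage of 0.05 equals the whole margin and exceeds the 0.04 gap between EMO-114 and EMO-118 in Table 7 (-0.12 against -0.08). It would also have to persist after about two weeks in each lens. This stands, and it points to the low end of the range. A reader might take 30% × 0.05 = 0.015, which gives about 68% or 82% power, but nothing in the documents supports those inputs.
- **Few such children may enrol.** The label covers starting ages 8 to 12, and half the sample is planned at 13 to 17. This stands. The share could be zero.
- **The run-in and the labelling help.** Habitual contact lenses are barred from the run-in onward, and blisters are over-labelled. This stands in part. A single-vision run-in gives the other children no experience of MiSight optics, and labelling does not disguise the lens on the finger or the eye.
- **MiSight is not the only possible prior exposure.** Earlier trials dispensed EMO lenses to children (section 1.5), and exclusion 10 looks back only 7 days. A reader might infer that prior experience can favour MiSight alone. The documents do not support that.

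Three other stronger readings also fail. The plan has no preference endpoint, and only one superiority hypothesis involves MiSight. The patient-reported outcomes are summarised descriptively by lens, so no formal claim rests on them. Loss of masking is a reasonable inference, not a documented fact. Its direction is unknown, so it cannot be offered as evidence of a false non-inferiority finding.

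**Conclusion.** The gap is real: current wearers of the control lens are eligible, and neither the sequence balancing nor the carryover term removes an effect tied to that lens. The consequence is modest and uncertain. If adaptation is the mechanism, the comparisons of EMO-118 and EMO-114 with MiSight are biased against the EMO lenses, and the cost is power. Under the illustrative shifts the loss at 50 completers runs from 2.0 to 14.0 points at correlation 0.3 (93.7% to between 91.7% and 79.7%) and from 0.8 to 7.5 points at 0.5 (98.5% to between 97.7% and 91.0%). These figures rest on assumed shares and advantages, on Table 8's SD and correlations, and on a true difference of 0. If no such child enrols, the loss is nil. Table 8 is arithmetically correct; it simply makes no allowance for this effect. This is a cheap improvement and does not invalidate the primary analysis.

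**What to change.** Add one exclusion, in the synopsis and in section 3.3, for current or recent habitual wear of MiSight or another myopia-control soft lens, including investigational EMO lenses. A lookback of 30 days would match exclusion 7, although the documents do not show that any particular interval removes adaptation or recognition. The criterion on soft lenses for astigmatism can stay as it is.

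If enrolment is under way, prespecify a sensitivity analysis in the stand-alone SAP, which section 14.1 says will be finalised before database lock. It should repeat the primary contrast and the patient-reported summaries without these wearers, identified from the habitual lens type recorded at step 1.4. Prior EMO wear would have to be identified from trial history.

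The cost is a slightly smaller recruitment pool, or one extra analysis that for MiSight wearers uses data already collected.
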